1 PROTOCOL REVISION HISTORY

19 February 2019 by PPD	
Final Protocol, Amendment 1
 
Period 1 was dosed on February 15, 2019 and 4 subjects experienced hypoglycemia events. These subjects had glucose values under 60 mg/dL postdose and were given additional glucose per the rescue interventions outlined in the protocol. Subjects' values recovered after lunch. However, due to the unknown interaction of LOXO-292 on repaglinide, additional safety measures will be implemented for Period 2.
 
The protocol is therefore being amended to (1) add glucose monitoring at 0.5, 1.5, and 3 hours postdose on Day 10 of Period 2, (2) increase the dose of glucose from 12 g to 16 g administered immediately following Day 10 dosing in Period 2, and (3) administer an additional 16 g of glucose at 1 hour postdose on Day 10 of Period 2 (approximately repaglinide Tmax).
 
Therefore Section 5 Synopsis, Summary of Study Design and Dosage, Dosage Form, Route, and Dose Regimen subsections, Section 6.2, Study Events Flow Chart, Period 2, Section 8.2.2 Rationale for the Dose Selection and Dose Regimen, Section 10.1 Overall Study Design and Plan, and Section 12.1 Treatments Administered were updated.
 
Section 13.2.5.2 was updated to include intramuscular glucagon as a rescue medication and to indicate that subject will be offered the placement of an IV catheter for rescue therapy.
 
In addition, the Note to File created on January 31, 2019 was incorporated into this amendment. Thus, the following statement was added at the end of the last sentence in Section 13.2.5.1: "In addition, the PI or designee may administer additional oral glucose, 16 g of glucose (4 x 4 g chewable tablets), if the blood glucose (monitored by finger stick) at any of the specified time points is < 60 mg/dL or at any other time based on evaluation of symptoms. For subjects with blood glucose < 60 mg/dL, intervention measurements outlined in protocol Section 13.2.5.2 will be followed."
 
Also, the first paragraph in Section 15.6 was updated to reflect the correct process with regards to record keeping and signing of the case report forms.

10 January 2019 by PPD	Final Protocol

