8.3 Risks and/or Benefits to Subjects

The dose of LOXO-292 administered in this study is not anticipated to induce any significant risk or benefit to subjects participating in this study as it does not exceed the highest daily total dose safely administered in the ongoing global Phase 1/2 Study (LOXO-RET-17001 [[Investigator's Brochure 2018](#)]).

The dose of repaglinide administered in this study is not anticipated to result in any significant risk to healthy subjects participating in the study as it is a single dose administered according to the dosing recommendations found in the full prescribing information for repaglinide as the starting dose in diabetic patients ([Full Prescribing information of repaglinide tablet, 2017](#)). Repaglinide can potentially lower glucose in healthy subjects. As a precaution, glucose will be administered to subjects following repaglinide dosing and glucose levels will be monitored up to 9 hours following each repaglinide administration during the study.

The safety monitoring practices employed by this protocol (i.e., 12-lead ECG, vital signs, clinical laboratory tests, glucose monitoring, AE monitoring, and physical examination) are adequate to protect the subjects' safety.

There will be no direct health benefit for study participants from receipt of study drug. An indirect health benefit to the healthy subjects enrolled in this study is the free medical tests received at screening and during the study.

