13.2.5 Glucose Monitoring

13.2.5.1 Blood Glucose

Blood glucose determinations will be performed as outlined in the Study Events Flow Chart ([Section 6](#)).

All measurements will be done with a glucose monitor and will be performed by finger stick.

Subjects who manifest hypoglycemic symptoms such as faintness, sweatiness, tachycardia, and headache, may have their blood glucose monitored by finger stick at any time during the study, at the discretion of the PI. In addition, the PI or designee may administer additional oral glucose, 16 g of glucose (4 x 4 g chewable tablets), if the blood glucose (monitored by finger stick) at any of the specified time points is < 60 mg/dL or at any other time based on evaluation of symptoms. For subjects with blood glucose < 60 mg/dL, intervention measurements outlined in protocol [Section 13.2.5.2](#) will be followed.

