TEAEs will be tabulated by system organ class and preferred term. Summary tables will include the number of subjects reporting the AE and as a percent of the number of subjects dosed by treatment and overall. Treatment B will be divided into two segments as B1 (Multiple doses of 160 mg LOXO-292 BID from Day 1 to Day 9) and B2 (Multiple doses of 160 mg LOXO-292 BID on Day 10 with a single dose of 0.5 mg repaglinide coadministered on the morning of Day 10) (see [Table 5.1](#)). Tables will also be presented by severity grade and relationship to study drugs. If a subject experienced the same TEAE at more than once with different level of severity grade for a given treatment, only the most severe one will be counted. Similarly, if a subject experienced the same TEAE at more than once with different level of drug relationship for a given treatment, only the one most closely related to the study drug will be counted.

Should any serious adverse events (SAEs) occur during the study, the SAEs will be displayed in a table and a narrative included in the Clinical Study Report.

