For all laboratory values that are numeric, descriptive statistics (n, mean, SD, minimum, median, and maximum) will be presented for each laboratory test by treatment and time point. Change from baseline in Treatment B (defined below) will also be summarized. Postdose unscheduled events or rechecks will not be summarized. Similarly, ET results will not be included in summaries.

For each laboratory test, a shift table will be developed comparing the frequency of the results at baseline (above normal, normal, or below normal) to postdose results. For urinalysis tests, the categories are normal and outside normal.

Baseline is Day -1 of Treatment A (Period 1) and Day 1 predose of Treatment B (Period 2), and is the last non-missing predose measurement prior to dosing of LOXO-292, including rechecks and unscheduled assessments.

7.5 **Blood Glucose Monitoring**

Blood glucose monitoring will be performed at the following time points:

Table 7.5 Glucose Monitoring Time Points

Period	Period Day	Study Hour
1	Day 1	0*
1	Day 1	1
1	Day 1	2
1	Day 1	4
1	Day 1	6
1	Day 1	9
2	Day 10	0*
2	Day 10	0.5
2	Day 10	1
2	Day 10	1.5
2	Day 10	2
2	Day 10	3
2	Day 10	4
2	Day 10	6
2	Day 10	9
* performed prior dosing		

Descriptive statistics will be reported for blood glucose determinations and change from baseline by treatment and time point. Baseline is Day 1 predose of Treatment A (Period 1) and Day 10 predose of Treatment B (Period 2) and is the last non-missing predose measurement prior to dosing of repaglinide including rechecks and unscheduled assessments. Postdose rechecks, unscheduled assessments, and ET results will not be used for calculation of descriptive statistics. All blood glucose results will be listed by subject.

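### Hypoglycemia counts under A and B2 are not directly comparable: scheduled glucose checks (5 versus 8) and scheduled glucose (12 g versus 32 g) both differ, and the planned tables neither match nor flag this

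*SAP*

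**What the plan says.** Table 7.5 in SAP 7.5, introduced by "Blood glucose monitoring will be performed at the following time points", gives these postdose hours:

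- Period 1, Day 1: 1, 2, 4, 6, 9.
- Period 2, Day 10: 0.5, 1, 1.5, 2, 3, 4, 6, 9.

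The difference comes from Amendment 1, written after Period 1 had been dosed. Its first item was to "add glucose monitoring at 0.5, 1.5, and 3 hours postdose on Day 10 of Period 2". The reason is in the revision history: "Period 1 was dosed on February 15, 2019 and 4 subjects experienced hypoglycemia events". It continues: "These subjects had glucose values under 60 mg/dL postdose and were given additional glucose".

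The same amendment changed the scheduled glucose. Protocol 12.1 and SAP 5 give 12 g after repaglinide in Period 1. On Day 10 of Period 2 they give 16 g after repaglinide and a further 16 g at about 1 h.

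Protocol 13.2.5.1 lets the investigator give more oral glucose if a reading "at any of the specified time points is < 60 mg/dL". It also says that subjects with hypoglycemic symptoms "may have their blood glucose monitored by finger stick at any time during the study, at the discretion of the PI".

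For adverse events, SAP 7.3 tabulates "the number of subjects reporting the AE and as a percent of the number of subjects dosed by treatment and overall", with Treatment B split into B1 (Days 1 to 9) and B2 (Day 10). For glucose, SAP 7.5 and Table 14.3.5.7 give descriptive statistics by treatment and time point, leaving out postdose rechecks and unscheduled readings. No planned table counts subjects with a reading below 60 mg/dL.

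**The concern.** Amendment 1 exists because hypoglycemia occurred on repaglinide alone and the effect of adding LOXO-292 was not known. A reader will naturally look at hypoglycemia under A and then under B2. The only planned display that gives a frequency for each is the TEAE table, and there the two columns come from different monitoring schedules. An asymptomatic low at 0.5, 1.5 or 3 h can be found by schedule only in Period 2. All three of those hours fall inside the 4 h postdose fast, and two lie within about half an hour of the expected repaglinide Tmax of 1 h.

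The columns also come from different glucose intakes, which would be expected to act in the opposite direction. A B2 excess could therefore partly reflect closer checking, and a similar or lower B2 count could hide a real increase. Nothing beside the tables warns of either.

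**Working it through.** **Inputs.** Check times: SAP Table 7.5. Added times: Amendment 1. Period 1 yield: 4 subjects, from the revision history. Denominator: 16 planned (SAP 3). The documents do not give the number dosed in Period 1, so 16 is assumed. Scheduled glucose: Protocol 12.1 and SAP 5.

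**Step 1: counts.** Period 1 has 5 postdose checks. Amendment 1 adds 3, and 5 + 3 = 8, which agrees with Table 7.5. Up to 3 h there are 2 checks (1, 2 h) against 5 (0.5, 1, 1.5, 2, 3 h). Both schedules end at 9 h, as Protocol 8.3 says: "glucose levels will be monitored up to 9 hours following each repaglinide administration during the study". So density differs and length does not.

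**Step 2: direction of the check effect.** The Period 1 times are a strict subset of the Period 2 times. With the same glucose curve and no rescue, any subject found low by the Period 1 schedule is also found by the Period 2 schedule. The added checks can raise the B2 count or leave it unchanged.

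**Step 3: size if checks are independent.** Let p be the chance of a low reading at one check, and suppose 4/16 = 25% is the yield of 5 checks.

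- p = 1 − 0.75^(1/5) = 0.056.
- Yield of 8 checks = 1 − 0.75^(8/5) = 0.369.
- Expected subjects = 16 × 0.369 = 5.9, a ratio of 0.369/0.25 = 1.48.
- The chance of 5 or more subjects of 16 is 0.76 at 36.9% and 0.37 at 25%.

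If checks within a subject are fully dependent, the expected number stays at 4.

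**Step 4: size by length of the dip.** Suppose an affected subject has one dip of duration D, starting at a time uniform on 0.25 to 3 h. Detection is the share of start times for which a scheduled check falls inside the dip. For D = 0.5 h:

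- A: starts in 0.5–1 or 1.5–2 h are caught, 1.0/2.75 = 36%.
- B2: starts in 0.25–2 or 2.5–3 h are caught, 2.25/2.75 = 82%.

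| D | A | B2 | 4 seen in A corresponds in B2 to |
|---|---|---|---|
| 0.5 h | 36% | 82% | 9.0 |
| 1 h | 64% | 100% | 6.3 |
| 1.5 h | 82% | 100% | 4.9 |
| 2 h or more | 100% | 100% | 4.0 |

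The last column is 4 × (B2 detection / A detection). Other start windows change the figures but not the pattern. With starts on 0.25–2 h, the B2 equivalent is 7.0 at D = 0.5 h and already 4.0 at D = 1 h. With starts on 0–4 h, it is 8.0 at 0.5 h, 5.3 at 1 h and 4.0 at 2 h.

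**Step 5: the opposing difference.** Scheduled glucose is 12 g in Period 1 and 16 + 16 = 32 g on Day 10. This would be expected to lower the number of B2 lows. The documents give nothing from which to size it, so it cannot be netted against Steps 3 and 4.

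**Step 6: after matching.** At 1, 2, 4, 6 and 9 h there are 5 checks against 5, and 2 against 2 in the first 3 h. The schedule is equal. The glucose difference remains, and a rescue triggered at an added time in Period 2 can raise the next common-time reading.

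**The case against.** **The counts need not differ, and more checking need not win.** A reader might infer that B2 must show more hypoglycemia through ascertainment even if LOXO-292 does nothing. The documents do not support that. Long dips are caught by either schedule, symptomatic ones can be checked at any time in both periods, and the extra scheduled glucose acts the other way. The revision history says values recovered after lunch. With a fast of at least 4 h, that may point to longer dips and so to the low end of the range, although onset times are not given. This objection stands, and the point is limited accordingly.

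**A low reading is not automatically a TEAE.** The 60 mg/dL line in Protocol 13.2.5.1 governs giving glucose, and the rescue steps in 13.2.5.2 are discretionary. Protocol 13.2.7.2 leaves the clinical significance of abnormal values to the investigator, with no glucose cut-off. This also stands. A route into the TEAE tables does exist, since the revision history itself calls Period 1 values under 60 mg/dL hypoglycemia events. But a matched count should use readings, not TEAE records, because TEAEs have onset times that need not fall on check times.

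**Much is already available.** Table 14.3.5.7 gives the minimum at each time, the listings give every reading with its hour, and glucose administration times are listed. No safety inference is planned, and A versus B2 is not the stated safety objective. All true. Yet a minimum at each hour does not give the number of subjects with any low reading, and a descriptive contrast without a note can still mislead.

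**Matching could mislead in turn.** The common-time readings in B2 follow more glucose than those in A. This is right, and it is why the matched row needs a footnote saying which way it leans.

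**Conclusion.** The raw A-versus-B2 hypoglycemia contrast is not interpretable as planned, because monitoring density and scheduled glucose both differ, with expected biases in opposite directions. The effect of the added checks alone ranges from none (dips of about 2 h or more) to about a doubling (0.5 h dips). Under independent checks it takes 4 of 16 to 5.9 of 16. The net direction is unknown.

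These sizes assume that 16 subjects were dosed in Period 1, that the 4 events were found at scheduled checks, and either independence between checks or a uniform dip start. The documents do not give dip duration. The counts of checks, the subset argument and the glucose amounts need no assumption.

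A common-time count is still worth having. The remaining differences identified here, more glucose and rescue after an added check, would be expected to lower the B2 count. A B2 excess at the common times could therefore not be put down to more frequent checking. The absence of an excess would not show the absence of an effect.

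**What to change.** In SAP 7.5 and Table 14.3.5.7, add two rows based on scheduled readings only:

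1. Number of subjects with any scheduled reading below the protocol's 60 mg/dL line at 1, 2, 4, 6 or 9 h, for A and for B2.
2. Number of B2 subjects whose only scheduled readings below that line were at 0.5, 1.5 or 3 h.

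Footnote this table and Tables 12-1 and 14.3.1.1 with the number of scheduled postdose checks (5 in A, 8 in B2) and the scheduled glucose (12 g in A, 32 g in B2). State there that the common-time row is expected to understate B2, because of the extra glucose and any rescue after an added check. Leave the TEAE counts themselves as planned.

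The cost is SAP wording, two rows and a footnote, with no new data. The downside is that neither row stands alone: a low found and treated at an added time may prevent one at a common time, so the rows must be read together. No change to monitoring, glucose dose or rescue rules is proposed.

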13.2.5.2 Rescue Intervention for Hypoglycemia

The following steps may be followed at the discretion of the PI:

The subject should be placed in a semi recumbent position. A conscious subject who is safely able to take food/drink by mouth should ingest 15-20 g of glucose. A glucose measurement should be taken 15 minutes later. If hypoglycemia persists, the treatment should be repeated.

Once the blood glucose concentration exceeds 70 mg/dL, the subject should consume a full meal containing at least 60 g of carbohydrate.

Following administration of food, blood glucose concentrations should be measured every 10-15 minutes for the first hour, every 30 minutes for an additional 2 hours, then hourly until blood glucose concentrations have been demonstrated to be stable within the normal range for at least 3 hours and, if present, symptoms have resolved. Oral supplementation may be attempted up to three times prior to intervention with intravenous (IV) dextrose. If a subject displays any signs/symptoms of instability, in the opinion of the PI, IV dextrose will be used immediately. If oral glucose and IV dextrose cannot be administered in an emergency situation, intramuscular glucagon will be used.

Subjects will be offered placement of an IV catheter in the event that dextrose is required. The IV catheter should be placed on the opposite arm from which the PK blood draws are taken.

If subject remains hypoglycemic and there has been no resolution of any associated symptoms despite the interventions described above, the subject should be rapidly transferred to a location where definitive care (i.e., an Emergency Room or Intensive Care Unit) is available.

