13.2.7.2 Monitoring

Subjects will be monitored from Screening (signing of informed consent) until EOS (or ET if the subject discontinues and does not complete a follow up call) for adverse reactions to the study drugs and/or study procedures. At the EOT (or ET) visit, subjects will be asked how they are feeling prior to check out from the CRU. During the EOS/follow-up phone call, subjects

will be queried with an open-ended question such as: 'How have you been feeling since your last visit?'

AEs (whether serious or non-serious), including abnormal laboratory test value(s), abnormal vital signs, and ECG abnormalities deemed clinically significant by the PI or designee will be evaluated by the PI or designee and treated and/or followed through EOS (or ET). AEs which are ongoing at the EOT or ET which are assessed as related to study drug by the PI (or designee) will be followed through the EOS. AEs which are ongoing at the EOS which are assessed as related to study drug may be continued to be followed until the symptoms or value(s) return to normal, or acceptable levels, as judged by the PI or designee and confirmed by the Sponsor.

Treatment of SAEs will be performed by a physician, either at the CRU or at a nearby hospital emergency room. Where appropriate, medical test(s) and/or examination(s) will be performed to document resolution of event(s). Outcome may be classified as death related to AE, not recovered or not resolved, recovered or resolved, recovered or resolved with sequelae, recovering or resolving, or unknown.

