2.2 Endpoints

Pharmacokinetics:

The following PK parameters will be calculated for repaglinide in plasma in Period 1, **CCI** and Period 2, **CCI**: AUC0-t, AUC0-inf, AUC%extrap, Cmax, Tmax, Kel, t_{1/2}, CL/F, and Vz/F.

The following PK parameters will be calculated for LOXO-292 in plasma in Period 2, on Day 1 (following morning dosing): AUC0-12, AUC0-t, Cmax, and Tmax; and on Day 10 (following morning dosing): AU τ , Cmax,ss, Tmax,ss, and CL,ss/F. Additionally, C_{trough} values will be assessed following the 2nd dose on **CCI**

CCI

Safety:

Safety endpoints will include 12-lead ECGs, physical examinations, vital signs, glucose monitoring, clinical laboratory tests, and AEs.

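### The finger-stick glucose table omits unscheduled postdose readings and counts no subjects below 60 mg/dL, so it can understate hypoglycemia and gives no Period 2 figure to set beside the four Period 1 cases

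*SAP*

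**What the plan says.** **Summary rule.** SAP 7.5 reports glucose and its change from baseline by treatment and time point. Of other readings it says: "Postdose rechecks, unscheduled assessments, and ET results will not be used for calculation of descriptive statistics". SAP 7 sets the same rule for all safety data and fixes the statistics as n, mean, SD, minimum, median and maximum. SAP 9.2 lists one finger-stick table, 14.3.5.7, and its visible rows are those six statistics.

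**Status of glucose.** SAP 2.2: "Safety endpoints will include 12-lead ECGs, physical examinations, vital signs, glucose monitoring, clinical laboratory tests, and AEs".

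**Where off-schedule readings come from.** Under Protocol 13.2.5.1, subjects with hypoglycemic symptoms "may have their blood glucose monitored by finger stick at any time during the study, at the discretion of the PI". Protocol 13.2.5.2, whose steps are at the investigator's discretion, adds readings after rescue: "A glucose measurement should be taken 15 minutes later", and after food, "blood glucose concentrations should be measured every 10-15 minutes for the first hour, every 30 minutes for an additional 2 hours".

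**The action line.** Protocol 13.2.5.1 allows extra oral glucose "if the blood glucose (monitored by finger stick) at any of the specified time points is < 60 mg/dL", or at other times on symptoms, and refers subjects below 60 mg/dL to the rescue section.

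**What has already happened.** The Protocol Revision History reports hypoglycemia in four subjects in Period 1: "These subjects had glucose values under 60 mg/dL postdose and were given additional glucose per the rescue interventions outlined in the protocol". It gives this, together with the unknown interaction, as the reason for the added Period 2 measures.

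**Where all readings appear.** SAP 7.5 sends every result to a by-subject listing, Appendix 16.2.8.2. The visible shell has no flag for low values.

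**The concern.** Leaving untimed readings out of by-time-point statistics is ordinary practice. The gap is that no other planned glucose summary uses them. The readings most closely tied to hypoglycemia, those taken because of symptoms or during rescue, are the ones the rule removes.

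The question raised by the amendment is about subjects: how many fell below 60 mg/dL, and how far. The table answers a different question, about the distribution of values at each scheduled time. Safety with and without coadministered repaglinide is a secondary objective. Without a planned count, the report would describe Period 1 by a number of affected subjects and Period 2 by means and minima. Under SAP 1, an analysis not in the SAP is out of scope and is described in the report as needed, so a count added later would be post hoc.

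**Working it through.** The plan gives no glucose threshold figure to reproduce. The only such number is the four subjects in the Protocol Revision History. The check is whether Table 14.3.5.7 can yield that kind of number.

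**Inputs**
- Planned subjects: 16 (SAP 3).
- Postdose checks (SAP Table 7.5): Period 1 at 1, 2, 4, 6, 9 h; Period 2 Day 10 at 0.5, 1, 1.5, 2, 3, 4, 6, 9 h.
- Planned glucose (SAP 5): 12 g in Period 1; 16 g + 16 g = 32 g on Day 10 of Period 2.
- Line: below 60 mg/dL (Protocol 13.2.5.1).

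**Step 1. Does one row of the table fix the count at that time?** Take two constructed sets of 16 values. Both contain 50, 66, 66, 66, 75, 75, 80, 82, 85, 88, 90, 95, 110. The other three values are:
- Set 1: 50, 56, 59. Sum 165; sum of squares 2500 + 3136 + 3481 = 9117.
- Set 2: 51, 54, 60. Sum 165; sum of squares 2601 + 2916 + 3600 = 9117.

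Equal sums and equal sums of squares give equal means and SDs.

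| | n | Mean | SD | Min | Median | Max | Below 60 |
|---|---|---|---|---|---|---|---|
| Set 1 | 16 | 74.56 | 16.93 | 50 | 75 | 110 | 4 |
| Set 2 | 16 | 74.56 | 16.93 | 50 | 75 | 110 | 3 |

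The six planned statistics are identical and the counts differ. A minimum below 60 shows only that at least one subject was below the line at that time.

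**Step 2. Can rows be joined into subjects?** Let k_j be the number below 60 at time j. The number of subjects ever below 60 lies between max(k_j) and the smaller of 16 and the sum of the k_j. With one low value at each of four times, that is between 1 and 4 subjects. The table does not give the k_j, and would not settle the count if it did.

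**Step 3. Which way does the exclusion act?** For a subject with scheduled readings S and unscheduled readings U, min(S and U together) ≤ min(S). Adding U can lower a subject's lowest value or leave it unchanged. It can raise the number of subjects ever below 60 or leave it unchanged. A scheduled-only summary can therefore understate depth and frequency, and cannot overstate them.

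**Step 4. What would the missing row look like for Period 1?** Four of 16 is 25.0% (exact 95% CI 7.3% to 52.4%). The denominator is an assumption, because the documents give the number planned and not the number dosed. With 15 it is 26.7% (7.8% to 55.1%), and with 14 it is 28.6% (8.4% to 58.1%). The documents contain no Period 2 count.

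**Step 5. Would counts be comparable between treatments?** Checks number 5 against 8. The shared times are 1, 2, 4, 6 and 9 h; those at 0.5, 1.5 and 3 h exist only in Period 2. Restricting to shared times equalises the number of checks, but not the planned glucose, 12 g against 32 g.

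**The case against.** **The SAP delivers what the protocol asks.** Protocol 14.3.2 asks for safety data, glucose included, to be summarised by treatment and collection time. SAP 7.5 does that, and the exclusion is uniform across laboratory, vital-sign and ECG data. This stands: there is no contradiction between the documents, and the case is for an addition.

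**The information is available.** With 16 planned subjects and one repaglinide day per period, a reader can count lows from Appendix 16.2.8.2. This stands as to the data. It does not supply a planned summary of a listed safety endpoint.

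**The adverse event tables cover it.** SAP 7.3 tabulates events separately for A, B1 and B2, and Protocol 13.2.7.1 counts an abnormal laboratory finding as a possible adverse event. This stands for lows recorded as events. No numeric glucose rule makes a low reading one; Protocol 13.2.7.2 describes adverse events as "including abnormal laboratory test value(s), abnormal vital signs, and ECG abnormalities deemed clinically significant by the PI or designee". A reader might infer that lows will go unrecorded. The documents do not support that: the revision history itself calls the four Period 1 cases hypoglycemia events.

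**Numeric triggers are scheduled.** The 60 mg/dL trigger for extra glucose refers first to specified time points, and those readings stay in the table. This stands: only lows, or deeper values, seen solely off schedule are lost from it. No document shows that any occurred. A reader might treat the frequency of rescue follow-up readings, or the spacing of scheduled checks, as a measure of missed lows. Neither is one; follow-up readings would be expected to be largely recovery values.

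**ECG thresholds are flagged, not counted.** SAP 7.7 flags QTcF limits in the listing only. That is a fair precedent for a glucose flag, which the fix includes. A count is also warranted here because a count of subjects prompted the amendment.

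**Redaction.** Time points and a block below the Table 14.3.5.7 shell are blacked out, so its footnotes cannot be fully checked. The text of SAP 7 and 7.5 on this point is legible and plans no count.

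**Conclusion.** The point holds as a limit of the summary. Table 14.3.5.7 can understate the depth and frequency of low glucose, and it cannot produce the number of subjects below 60 mg/dL in either period. The adverse event tables supply that number only for lows recorded as events.

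No size of understatement can be given, because the documents do not say whether any low was seen only off schedule. The conclusion rests on the legible text of SAP 7 and 7.5, and on the assumption that no redacted part of the shell adds a threshold count.

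A reader might infer that hypoglycemia data are lost, or that the treatment comparison is biased. Neither follows. All readings are listed, scheduled lows show in the minima, the SAP plans no inferential test of safety data, and the primary PK analysis does not use these readings. This is a cheap and worthwhile improvement, not a flaw in the trial's main result.

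**What to change.** Keep the by-time-point statistics as planned, and make these additions:

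1. By treatment, n (%) of subjects with any postdose reading below 60 mg/dL through 9 h after repaglinide, using scheduled and unscheduled readings, with the lowest value of each such subject. The 9 h limit matches the last check in SAP Table 7.5.
2. Beside it, the same count from the shared scheduled times only (1, 2, 4, 6, 9 h).
3. A flag on readings below 60 mg/dL in Appendix 16.2.8.2.
4. A footnote giving the postdose checks (5 versus 8) and the planned glucose (12 g versus 16 g + 16 g).

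**Cost.** One small descriptive table, one listing flag and one footnote, all from readings already collected and listed.

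**Downside.** Unscheduled readings are symptom-driven, and Period 2 has more checks and more glucose. The shared-time count removes only the difference in check numbers. A low found at 0.5, 1.5 or 3 h in Period 2 may also prompt glucose that lifts the next shared reading. Both counts should be labelled descriptive and not read as an unconfounded comparison of B with A. Nothing here bears on dosing, rescue or monitoring.
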